### 3.2 Secondary Endpoints

- Survival rate of study implants evaluated at visit 6 (Initial implant loading)
- Success rate of study implants evaluated at visit 6 (Initial implant loading)
   Crestal bone level loss as well as the criteria according to Buser et al. will be used to define the survival and success rate of study implants.

### 4 Study Design

### 4.1 Type and Design of Study

This is a prospective, randomized, controlled, open label study, conducted at two sites in Germany and Switzerland comparing two treatment groups.

#### 4.2 Indications for use

The package inserts (instructions for use) provide detailed information and instructions for the usage of the investigational bone substitute material and membrane as well as for the comparator products.

All used products are CE marked.

### 4.3 Study Treatments

Before entering into the study, each subject has to sign an informed consent. A subject is enrolled if she/he meets all inclusion criteria and at the same time does not meet any exclusion criteria. Enrolled subjects will be scheduled for sinus elevation. At surgery subject eligibility will again be evaluated according to secondary exclusion criteria. Subjects who do not meet any secondary exclusion criteria are randomized to one of the following groups:

- a) Sinus floor elevation with Straumann® VivOss™
- b) Sinus floor elevation with Geistlich Bio-Oss®

After a healing time of 1-2 weeks, sutures are removed, and the wound healing is evaluated. After a healing time of 6 months, an intermediate osteotomy for the dental implant placement is done by means of a trephine burr in such a way that the biopsy is harvested at the same time. Dental implant placement will be completed according to the standard procedure of the clinic. After a healing time of 1-2 weeks, the sutures are removed and the wound healing is evaluated. 4 months after implant placement the implant is initially loaded and the survival as well as the success rate will be evaluated.

Version 6.0 Page 14 of 47

### 4.4 Number of Subjects

This study will be performed in two clinical centres, one in Germany and one in Switzerland; these centres are expected to recruit 50 subjects in total, 25 subjects in test group, 25 subjects in control. Planned subject recruitment period is 3 months. The recruitment is competitive. Recruitment will be stopped as soon as recruitment is complete.

### 4.5 Study Duration

The primary endpoint will be assessed 6 months  $\pm$  7 days after sinus floor elevation. The entire study duration for each enrolled subjects is 9-14 months (screening to last visit).

The entire study duration from first patient in until last patient out will be approximately 17 months.

### 5 Study Population

Generally healthy female and male subjects, who are at least 18 years of age and are willing to participate in this study and who would benefit from a prosthetic reconstruction with a dental implant but need a sinus floor elevation in either one or both sinuses.

#### 5.1 Inclusion Criteria

The subjects will be evaluated for initial study eligibility during the screening visit. Those subjects who appear eligible according to the inclusion/exclusion criteria will be asked to sign an informed consent form to be enrolled into the study. The following criteria must be met for inclusion in the study:

- 1. Subject must have voluntarily signed the informed consent before any study related action
- 2. Males and females with at least 18 years of age (including 18 years)
- 3. Subject needs augmentation procedure in the sinus to prepare for implant placement.
- 4. Subject must have a residual bone height of 2 to 4 mm.
- 5. Adequate oral hygiene ((Full mouth plaque index (O'Leary, et al. 1972 ) <25%) at baseline
- 6. Adequate control of inflammation ((full mouth bleeding on probing (Ainamo and Bay 1975)) ≤25% at baseline

#### 5.2 Exclusion Criteria

If any of the following criteria are met, the subject must be excluded from the study:

- 1. Systemic disease that would interfere with bone or wound healing and dental implant therapy (e.g. uncontrolled diabetes)
- 2. Systemic disease that would interfere with bone or wound healing and dental implant therapy (e.g. uncontrolled diabetes)
- 3. Any contraindications for general bone grafting and oral surgical procedures
- 4. Any anomalies of the sinus that could interfere with planned procedures
- 5. History of local irradiation therapy
- 6. Local inflammation, including untreated periodontitis
- 7. Medical conditions requiring chronic high dose steroid therapy

Version 6.0 Page 15 of 47

- 8. Treatment with an investigational drug or device within a 30 day period immediately prior to surgery at visit 2, or expected participation in any other investigational drug or device study during the conduct of this trial.
- 9. Antibiotic treatment or anti-inflammatory treatment within 4 weeks prior to surgery
- 10. History of alcoholism or drug abuse
- 11. Immunocompromised subjects
- 12. Subjects who smoke >10 cigarettes per day or tobacco equivalents or chew tobacco
- 13. Conditions or circumstances, in the opinion of the investigator, which would prevent completion of study participation or interfere with analysis of study results, such as history of non-compliance or unreliability
- 14. Physical or mental disabilities that would interfere with the ability to perform adequate oral hygiene
- 15. Current pregnancy (pregnancy test) and breastfeeding women

### 5.3 Secondary exclusion criteria at sinus floor elevation

If the following criteria is met at sinus floor elevation, the subject must be excluded from the study:

1. Defects of the Schneider Membrane

### 5.4 Treatment Groups

In total 50 subjects will be randomize equally into test or control group (25 patients in each group).

The subjects in the test group receive sinus floor elevation with HA/TCP 10:90 (*Straumann*® *VivOss*™) via a lateral approach. In the comparator group, subjects receive sinus floor elevation with demineralized bovine mineral (Bio-Oss®) via a lateral approach.

Both groups follow the same schedule of assessments.

### 6 Investigational Device(s)

### 6.1 General Description of the Investigational Devices

All investigational devices used in this study are CE marked.

**Straumann® VivOss™** Straumann® VivOss™, is a synthetic bone graft substitute in granulated form. It consists of > 90% TCP (Tri-Calcium-Phosphate  $-Ca_3(PO_4)_2$ ) and < 10% Hydroxyapatite ( $Ca_{10}(PO_4)_6$  (OH)2). The granules have a size of 250-1000 µm.

Straumann® VivOss™ is both osteoconductive and has a porous trabecular structure that resembles the interconnected porosity of human cancellous bone. Straumann® VivOss™ induces and guides the three dimensional regeneration of bone in the defect site into which it is implanted. It's intended to be used for applications in oral and maxillofacial surgery and dentistry for filling or reconstruction of multiple walled (artificial or degenerative) bone defects.

The Sponsor supplies the product. It shall be used according to the instructions of the manufacturer.

Version 6.0 Page 16 of 47

### 6.1.1 Instruction for Use, Handling, and Labelling

For the instructions for use, handling and labelling, the investigator has to refer to the instruction for use of the study products. In case of any questions, comments or doubts, the investigator can contact Institut Straumann AG.

In the event of a problem with the study product the monitor or the study manager should be informed immediately. In case of missing or lost study products all discrepancies have to be documented.

### 6.1.2 Storage

The study products provided by the Sponsor are to be used for the subjects enrolled in the clinical study only. The study products should be stored in its original container until used and as it is indicated in the package insert.

Handling of unused study products can be found under section 6.3 Device Accountability.

### 6.1.3 Risks and Benefits of the Investigational Device and Clinical Investigation

The investigational and control devices used in this study are CE marked. The clinical procedures performed are standard procedures.

The risk analyses for the investigational devices were conducted according to ISO 14971.

It can be stated that the risk from the investigational devices is low and acceptable, and the identified risk hazards from the devices are justified when considered against the significant clinical benefits provided. The investigational devices raise no new questions for safety and effectiveness as compared to similar devices. The investigator follows the instructions for use recommended by the manufacturer.

The possible risks and discomforts that may be associated with participation in this study are no different than having the same procedure (Sinus floor augmentation and placement of dental implants in a 2 stage approach) done without participation in this study. The following risks and adverse events can occur:

- General risks that exist with surgical procedures in the oral cavity: Bleeding and bruising, pain and swelling after the surgical procedure. Infections in the soft and hard tissue, delayed healing, recession of the gum and/or bone, temporary or permanent nerve damage in the jaw, oro-sinus or oro-nasal fistulas and possible rejection are very rare.
- General risks that exist with a surgical procedure using barrier membranes and can therefore not be completely ruled out: soft tissue dehiscence (tissue damage), haematoma, pain, increased sensitivity and redness due to inflammation
- Gingival inflammation (oral hygiene dependent): Oral hygiene instructions are given and oral hygiene procedures performed to prevent gingival inflammation.
- The following are examples of complications that can generally occur with a surgical procedure in the oral cavity and can therefore not be completely ruled out:
  - Slight pain and tenderness the first days after surgery
  - Slight swelling and redness the first days after surgery
- Pregnancy during the study, in particular at surgery, and the use of x-rays / CBCTs during pregnancy constitutes an additional risk to the foetus. Therefore neither

Version 6.0 Page 17 of 47

pregnant women nor women who plan to become pregnant must take part in this study.

The bone biopsy will be retrieved following a minimally invasive procedure during conventional dental implant bed preparation. The bone biopsy is retrieved by means of a trephine burr with a inner diameter of 2.8 mm during implant bed preparation. The dental implant bed preparation is finalized and the dental implant placed according to the protocol.

Dental implants can improve the bite and chewing ability, as well as the aesthetics and the feeling to have natural teeth. In addition, the subject can profit from an intensive and regular dental care as participant.

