### 7.2 Pregnancy Test

Women of childbearing potential (women who are not surgically sterile or postmenopausal defined as amenorrhea for >12 months) must perform a pregnancy test (urine based) during screening. The test result must be documented in the source data.

During the study it is recommended to use highly effective contraceptive method (failure rate less than 1% per year) such as injectable, combined oral contraceptives or hormonal intrauterine devices (IUDs).

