#### 9.14 Pregnancy

If a female subject becomes pregnant during the course of the study, the study visits should be completed as scheduled. Any study assessments that could potentially interfere with the pregnancy should be avoided until after the pregnancy (e.g. CBCTs, radiographs, etc.). The pregnancy should be recorded as an adverse event, whereas the start of pregnancy will be recorded as the start date of the AE and the date of child birth will be recorded as the end date.

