### 12 Regulatory and Ethical Requirements

### 12.1 Basic requirements

The principal investigator/co-investigator shall confirm the eligibility of the subject by the screening test and confirm the conformity to the inclusion/exclusion criteria at the subject enrolment.

Also, the principal investigator/co-investigator shall keep knowledge about the subject's health condition by retaining the communication path to the subject for the emergency during the follow-up period, etc. Also, he/she shall make an effort to collect and transfer the safety information relevant to the investigational device with the cooperation of the relevant peoples involved to this study. In case of the occurrence of the adverse event, the principal investigator/co-investigator shall provide an appropriate treatment to ensure the subject's safety.

A Sponsor shall collect and examine information that is necessary for properly conducting a clinical trial, with respect to matters concerning the quality, efficacy, and safety of the investigational device and provide the head of the medical institution with such information.

Whenever the Sponsor finds any of the items such as disease, injury or death suspected due to adverse device effect, infection due to the investigational device or other events relates to the effectiveness or safety of the investigational device, Sponsor shall promptly notify the principal investigator and the head of the medical institution thereof.

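### Section 6.1.3 bars women who plan to become pregnant, but the exclusion lists that decide enrolment leave them out, so a site could enrol one.

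*Combined protocol and SAP*

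**What the plan says.** Section 6.1.3 gives the risk and the rule. Pregnancy during participation, particularly when surgery takes place, and imaging while pregnant are named as added risks to the foetus. The section then says that neither "pregnant women nor women who plan to become pregnant must take part in this" study. The sentence is awkward, but its intent to bar both groups is plain.

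The criteria are narrower. Section 5.2 item 15 reads "Current pregnancy (pregnancy test) and breastfeeding women", and synopsis item 14 has the same words. (The item numbers differ by one because 5.2 prints its first criterion twice.)

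Enrolment runs on the criteria. Section 4.3 states: "A subject is enrolled if she/he meets all inclusion criteria and at the same time does not meet any exclusion criteria". Section 7.5 sends the reader to 5.1 and 5.2 only. Section 12.1 has the investigator "confirm the conformity to the inclusion/exclusion criteria at the subject enrolment".

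On testing, section 7.2 says that women of childbearing potential "must perform a pregnancy test (urine based) during screening". It recommends, but does not require, highly effective contraception during the study. The Schedule of Assessment shows no later pregnancy test.

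**The concern.** A prohibition that appears only in a risk narrative is easily missed by staff who screen from a list. Here the two places also give different answers for the same woman: the enrolment rule admits her and the risk section forbids her.

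What is at stake is protection of the foetus. Current pregnancy is handled by both lists and by the screening test. The uncovered case is a woman who is not pregnant at screening and intends to conceive while in the study. Sinus elevation at Visit 2 is followed by a second operation, biopsy and implant placement, at Visit 4. Section 6.1.3 singles out surgery as the main worry, and its bar on planned pregnancy is the only enrolment rule directed at this case.

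**Working it through.** No figure in the plan needs reproducing. The check compares texts, followed by a short calculation of the exposure window.

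**Step 1: where planned pregnancy appears.**

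| Place | Current pregnancy | Planned pregnancy |
|---|---|---|
| 6.1.3, risks and benefits | barred | barred |
| Synopsis, exclusion item 14 | excluded | not mentioned |
| 5.1, inclusion | not mentioned | not mentioned |
| 5.2, exclusion item 15 | excluded | not mentioned |
| 5.3, secondary exclusion at surgery | not mentioned (membrane defects only) | not mentioned |

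**Step 2: which text decides.** Sections 4.3, 7.5 and 12.1 all rely on the inclusion and exclusion criteria. None refers to 6.1.3. A woman with a negative test who says she intends to conceive fails none of the listed pregnancy criteria.

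**Step 3: does another provision close the gap?**

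- 5.2 item 13 (synopsis item 12) excludes for "Conditions or circumstances, in the opinion of the investigator, which would prevent completion of study participation or interfere with analysis of study results". This depends on the investigator's opinion, and it concerns completion and analysis, not harm to a foetus. Section 9.14 has a subject who becomes pregnant keep her visit schedule, so an investigator could reasonably decide that pregnancy does not prevent completion.
- 7.2 detects an existing pregnancy, not an intention. Its contraception advice is optional, and a woman trying to conceive would not follow it.
- 9.14 says: "Any study assessments that could potentially interfere with the pregnancy should be avoided until after the pregnancy". This applies once a pregnancy exists, so it is not an enrolment rule. It speaks of assessments and does not clearly settle whether the Visit 4 surgery goes ahead.

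**Step 4: the exposure window.** The inputs come from the Schedule of Assessment. The pregnancy test is at Visit 1, 0 to 14 days before Visit 2. Visit 4 is 6 months ± 7 days after Visit 2. Visit 6 is 4 months ± 1 month after Visit 4. The assumption is 1 month = 365.25/12 = 30.44 days, so 6 months = 182.6 days, 3 months = 91.3 days and 5 months = 152.2 days.

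- Test to Visit 4, shortest: 0 + 182.6 − 7 = 175.6 days.
- Test to Visit 4, longest: 14 + 182.6 + 7 = 203.6 days.
- Test to Visit 6, shortest: 175.6 + 91.3 = 266.9 days.
- Test to Visit 6, longest: 203.6 + 152.2 = 355.8 days.

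A planned conception can therefore fall well before the second operation with no scheduled test in between.

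**The case against.** The strongest reply is that 6.1.3 already binds. It is current protocol text in mandatory wording, section 12.4 requires compliance with the whole protocol, section 8.6 permits no deviations, and monitors check adherence. On that reading the rule is merely stated once and not repeated, and a site goes wrong only by overlooking it. It is true that 6.1.3 binds. But 4.3 and section 5 bind as well, and they give the opposite answer, so a general duty to follow the protocol does not resolve the conflict.

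A second reply is that other safeguards deserve weight: the screening test, the contraception recommendation, the deferral of assessments in 9.14, and imaging that the schedule limits to clinical need. The duty in 7.1 to explain hazards before consent also counts. The consent form and the eligibility page of the case report form are not among the documents, so a site may in practice be prompted to ask about planned pregnancy. These measures reduce the risk. None of them carries the bar into the criteria.

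A third reply is that the day counts do not measure the defect. That is right. They show how long a woman goes without a scheduled test, they apply equally to unplanned pregnancy, and the proposed fix leaves them unchanged. They should be read only as the window in which a planned pregnancy could meet the second surgery.

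Finally, 6.1.3 itself says that participation carries no more risk than the same procedure outside the study. That limits the weight of the point, but the same section still imposes the bar.

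**Conclusion.** The point holds. Planned pregnancy is barred in 6.1.3 and is absent from every list used to decide enrolment, so the protocol contradicts itself on whether such a woman may take part.

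The number affected cannot be derived from the documents and is probably small, since it covers only women who plan a pregnancy during participation. For each of them the window from the only scheduled test is about 176 to 204 days to the Visit 4 surgery and about 267 to 356 days to Visit 6, given a 30.44-day month.

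This is an eligibility and safety inconsistency. It does not touch sample size, power or the primary analysis. Any effect on the implant-success endpoint is secondary, because 9.14 postpones radiographs and does not cancel them. The correction should be made, but the trial's validity does not depend on it.

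**What to change.** Amend section 5.2 item 15 and synopsis item 14 to read: *Current pregnancy (pregnancy test), breastfeeding, or planning to become pregnant during the study.* Section 6.1.3 can stay as it is, and consistency needs no change to 7.2.

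The cost is one phrase in two list items, made through a protocol amendment with the approvals that section 13.3 requires. It adds no visit, test or procedure. A few more women may become ineligible; the number is unknown, but they are women whom 6.1.3 already forbids.

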### 6.2 Comparators

All comparators used in this study are CE marked. The Sponsor supplies the products.

Geistlich Bio-Oss®

The control device is *Geistlich Bio-Oss*® spongiosa granules (Geistlich Pharma AG, Wolhusen, Switzerland), 0.25-1 mm in diameter. It's a natural bone mineral of bovine origin. It shall be used according to the instructions of the manufacturer.

### 6.3 Additionall products used in the study

Geistlich Bio-Gide®

Geistlich Bio-Gide® is a pure collagen matrix. The collagen is extracted from veterinary certified pigs and is carefully purified. It shall be used according to the instructions of the manufacturer.

#### 6.4 Device Accountability

The investigator has to confirm the receipt of the study products and ensures secure and proper storage. After treatment of the last subject, remaining study products that have not been used in the study should be returned to the Sponsor or destroyed on site according to the sites standard procedures. The investigator should maintain accountability records of all study products received, used, and returned during the course of the study.

### 6.5 Device Complaints

Defects in the investigational devices should be reported to the Sponsor by the investigator immediately upon discovery.

Defects in the comparators should be reported by the investigator to the manufacturer of the comparators.

### 7 Study Procedures

#### 7.1 Informed Consent

It is the responsibility of the investigator, or a person designated by the investigator (if acceptable by local regulations), to obtain written informed consent from each subject participating in this study, after adequate explanation of the aims, methods, anticipated benefits and potential hazards of the study. The investigator will also explain to each subject

Version 6.0 Page 18 of 47

any alternative procedures. The investigator or designee must also explain that the subjects are completely free to refuse to enter the study or to withdraw from it at any time, for any reason and that they will be offered an alternative treatment related to their dental condition. Subjects will be advised of the need for the prescribed follow-up visits for their ongoing care and well-being and for the collection of relevant study data. All subjects must be willing to return to the clinical centre to complete such visits. The written informed consent has to be obtained from all subjects before any study related procedures are performed. This Institutional Review Board (IRB)/ Ethics Committee (IEC) approved consent form must be signed and dated by the subject and the investigator. If the investigator intend to start with any study related procedure on the same day the subject signed the informed consent, the investigator and the subject have to indicate the exact time of the informed consent on the informed consent form.

If new safety information results in significant changes in the risk/benefit assessment, the consent form should be reviewed and updated if necessary. All subjects (including those already being treated) should be informed on the new information, given a copy of the revised form and give their consent to continue in the study.

Investigators should keep one original signed informed consent document in the investigators file or the CRF folder and hand out a second signed informed consent document to the subject.

